10.4.2.2 Contraception guidance for female subjects

- If locally required, acceptable contraceptive methods are limited to those which inhibit ovulation as the primary mode of action.
- Females of childbearing potential enrolled in this protocol must agree to use two reliable forms of contraception simultaneously or to practice complete abstinence from heterosexual intercourse during the following time periods related to this study:
 - For at least 28 days before starting study treatment,
 - And throughout the entire duration of pomalidomide treatment,
 - And during dose interruptions,
 - And for at least 5 months after study treatment discontinuation.
- The two methods of reliable contraception must include one highly effective method and one additional effective (barrier) method.
- Highly effective contraception with low user dependency is preferred.
- A FCBP must be referred to a qualified provider of contraceptive methods if needed.

CONTRACEPTIVES^a ALLOWED DURING THE STUDY INCLUDE:

Highly effective methods^b that have low user dependency *Failure rate of <1% per year when used consistently and correctly.*

- Implantable progestogen-only hormone contraception associated with inhibition of ovulation.
- Intrauterine device (IUD).
- Intrauterine hormone-releasing system (IUS).
- Bilateral tubal occlusion.
- Azoospermic partner (vasectomized or due to a medical cause).

Azoospermia is a highly effective contraceptive method provided that the partner is the sole sexual partner of the woman of childbearing potential and the absence of sperm has been confirmed. If not, an additional highly effective method of contraception should be used.

Note: documentation of azoospermia for a male participant can come from the site personnel's review of the participant's medical records, medical examination, or medical history interview.

Highly effective methods^b that are user dependent *Failure rate of <1% per year when used consistently and correctly.*

- Combined (estrogen- and progestogen-containing) hormonal contraception^c associated with inhibition of ovulation.
 - Intravaginal.
 - Transdermal.
 - Injectable.
- Progestogen-only hormone contraception associated with inhibition of ovulation.
 - Oral.
 - Injectable.
- Sexual abstinence.

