Sexual abstinence is considered a highly effective method only if defined as refraining from heterosexual intercourse during the entire period of risk associated with the study intervention. The reliability of sexual abstinence needs to be evaluated in relation to the duration of the study and the preferred and usual lifestyle of the participant.

- a Contraceptive use by men or women should be consistent with local regulations regarding the use of contraceptive methods for those participating in clinical studies.
- b Failure rate of <1% per year when used consistently and correctly. Typical use failure rates differ from those when used consistently and correctly.
- c A patient can use 'oral' combination if they have discontinued pomalidomide.
As per pomalidomide Summary of Product Characteristics (SmPC), combined oral contraceptive pills are not recommended because of the increased risk of venous thromboembolism in patients with multiple myeloma taking pomalidomide and dexamethasone.

Note: Periodic abstinence (calendar, ovulation, symptothermal, post-ovulation methods), withdrawal (coitus interruptus), spermicides only, and lactational amenorrhea method (LAM) are not acceptable methods of contraception for this study. Male condom and female condom should not be used together (due to risk of failure from friction).

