10.4.2.3 Contraception for male subjects

Male subjects with heterosexual partners of reproductive potential (FCBP) are eligible to participate if they agree to use the following during the protocol defined timeline:

- Refrain from donating sperm,
and
- At least 1 of the following conditions applies:
 - Are and agree to remain abstinent from penile-vaginal intercourse on a long term and persistent basis, when this is their preferred and usual lifestyle,
or
 - Agree to use a male condom plus an additional contraceptive method with a failure rate of <1% per year (see table for female subjects) while taking pomalidomide/isatuximab, during dose interruptions and for at least 28 days after the last dose of pomalidomide or 5 months following the last dose of isatuximab, whichever occurs last, even if he has undergone a successful vasectomy.

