10.4.4 Additional precautions during and after study participation

10.4.4.1 Female participants

At each visit, the Investigator must confirm with the FCBP that she is continuing to use a highly effective form of contraception (see definition above) at each visit during the time that birth control is required.

If pregnancy or a positive pregnancy test does occur in a study participant, pomalidomide and isatuximab must be immediately discontinued.

Pregnancy testing and counseling must be performed if a participant misses her period or if her pregnancy test or her menstrual bleeding is abnormal. Pomalidomide and isatuximab treatment must be temporarily discontinued during this evaluation.

Females must agree to abstain from breastfeeding during study participation and for at least 28 days after discontinuation of pomalidomide or 5 months after discontinuation of isatuximab, whichever occurs last.

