2.5.2. During and After Study Participation

2.5.2.1. Female Subjects

- Females of childbearing potential with regular or no menstrual cycles must agree to have pregnancy tests weekly for the first 28 days of study participation and then every 28 days while taking pomalidomide, at study discontinuation, and at Day 28 following the last dose of pomalidomide.
- Females of childbearing potential with irregular menstrual cycles must agree to have pregnancy tests weekly for the first 28 days of study participation and then every 14 days while taking pomalidomide, at study discontinuation, and at Days 14 and 28 following the last dose of pomalidomide.
- At each visit, the Investigator must confirm with the FCBP that she is continuing to use two reliable methods of birth control if not committing to complete abstinence, or confirm commitment to complete abstinence.
- If a FCBP considers the need to change or to stop a method of contraception, the Investigator must be notified immediately.
- Counseling about pregnancy precautions and the potential risks of fetal exposure must be conducted at a minimum of every 28 days.
- If pregnancy or a positive pregnancy test does occur in a subject, pomalidomide must be immediately discontinued.
- Pregnancy testing and counseling must be performed if a subject misses her period or if her pregnancy test or her menstrual bleeding is abnormal. Pomalidomide must be discontinued during this evaluation.
- Females must agree to abstain from breastfeeding while taking pomalidomide and for at least 28 days after the last dose of pomalidomide.

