3. POMALIDOMIDE EDUCATION AND COUNSELING GUIDANCE DOCUMENT FOR FEMALE SUBJECTS

To be completed prior to each dispensing of pomalidomide.

Protocol Number: _____

Subject Name (Print): _____ DOB: _____ / _____ / _____ (dd/mmm/yyyy)

Check one risk category:

- FCBP (Female of childbearing potential): a female who: 1) has achieved menarche (first menstrual cycle) at some point, 2) has not undergone a hysterectomy (the surgical removal of the uterus) or bilateral oophorectomy (the surgical removal of both ovaries) or 3) has not been naturally postmenopausal (amenorrhea following cancer therapy does not rule out childbearing potential) for at least 24 consecutive months (ie, has had menses at any time during the preceding 24 consecutive months)
- NOT FCBP

3.1. Female of Childbearing Potential:

1. I have verified and counseled the subject regarding the following:

- Potential risk of fetal exposure to pomalidomide: A teratogenic potential of pomalidomide in humans cannot be ruled out. If pomalidomide is taken during pregnancy, it may cause birth defects or death to any unborn baby. Females are advised to avoid pregnancy while taking pomalidomide. Females of childbearing potential must agree not to become pregnant while taking pomalidomide.
- That the required pregnancy tests performed are negative.
- The subject confirmed that she is using TWO reliable methods of birth control at the same time, or complete abstinence (True abstinence is acceptable when this is in line with the preferred and usual lifestyle of the subject. Periodic abstinence [eg calendar, ovulation, symptothermal or post-ovulation methods] and withdrawal are not acceptable methods of contraception.) from heterosexual contact (at least 28 days prior to receiving pomalidomide, while receiving pomalidomide, during dose interruptions and for at least 28 days after the last dose of pomalidomide).

One highly effective method and one additional method of birth control must be used AT THE SAME TIME. The following are examples of highly effective and additional effective methods of contraception:

- Examples of highly effective methods:
 - Intrauterine device (IUD)
 - Hormonal (birth control pills, injections, implants, levonorgestrel-releasing intrauterine system [IUS], medroxyprogesterone acetate depot injections, ovulation inhibitory progesterone-only pills [e.g. desogestrel])

Global PPP Pomalidomide Adult
Celgene Corporation

Protocol [#]
Version 4.0 – Approved: 30 October 2014

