Effective Date: 19 December 2014

- Tubal ligation
 - Partner's vasectomy
 - Examples of additional effective methods:
 - Male condom
 - Diaphragm
 - Cervical Cap
- The subject confirmed that even if she has amenorrhea she must comply with advice on contraception.
- Pregnancy tests before, during administration of pomalidomide and at the last dose of pomalidomide, even if the subject agrees not to have reproductive heterosexual contact.
- Frequency of pregnancy tests to be done:
 - Two pregnancy tests will be performed prior to receiving pomalidomide, one within 10 to 14 days, and a second within 24 hours of the start of pomalidomide.
 - Every week during the first 28 days of this study and a pregnancy test every 28 days while the subject is taking pomalidomide if menstrual cycles are regular.
 - Every week during the first 28 days of this study and a pregnancy test every 14 days while the subject is taking pomalidomide if menstrual cycles are irregular.
 - If the subject missed a period or has unusual menstrual bleeding.
 - When the subject is discontinued from the study and at Day 28 after the last dose of pomalidomide if menstrual cycles are regular. If menstrual cycles are irregular, pregnancy tests will be done at discontinuation from the study and at Days 14 and 28 after the last dose of pomalidomide.
- The subject confirmed that she will stop taking pomalidomide immediately in the event of becoming pregnant and to call her study doctor as soon as possible.
- The subject confirmed that she has not and will not breastfeed a baby while taking pomalidomide and for at least 28 days after the last dose of pomalidomide.
- The subject has not and will never share pomalidomide with anyone else.
- The subject has not and will not donate blood while taking pomalidomide, during dose interruptions and for at least 28 days after the last dose of pomalidomide.
- The subject has not and will not break, chew, or open pomalidomide capsules at any point.
- The subject confirmed that she will return unused pomalidomide capsules to the study doctor.

2. I have provided the Pomalidomide Information Sheet to the subject.

3.2. Female Not of Childbearing Potential (Natural Menopause for at Least 24 Consecutive Months, a Hysterectomy, or Bilateral Oophorectomy):

1. I have verified and counseled the subject regarding the following:

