4. POMALIDOMIDE EDUCATION AND COUNSELING GUIDANCE DOCUMENT FOR MALE SUBJECTS

To be completed prior to each dispensing of pomalidomide.

Protocol Number: _____

Subject Name (Print): _____ DOB: _____ / _____ / _____ (dd/mmm/yyyy)

1. I have verified and counseled the subject regarding the following:

- Potential risk of fetal exposure to pomalidomide: A teratogenic potential of pomalidomide in humans cannot be ruled out. If pomalidomide is taken during pregnancy, it may cause birth defects or death to any unborn baby.
- The subject confirmed that he has practiced complete abstinence (True abstinence is acceptable when this is in line with the preferred and usual lifestyle of the subject. Periodic abstinence [eg calendar, ovulation, symptothermal or post-ovulation methods] and withdrawal are not acceptable methods of contraception.) or used a condom when engaging in sexual contact (including those who have had a vasectomy) with a pregnant female or FCBP, while taking pomalidomide, during dose interruptions and for at least 28 days after the last dose of pomalidomide.
- The subject confirmed that he has not impregnated his female partner while in the study.
- The subject confirmed that he will notify his study doctor if his female partner becomes pregnant and the female partner of a male subject taking pomalidomide confirmed that she will call her healthcare provider immediately if she becomes pregnant.
- The subject has not and will never share pomalidomide with anyone else.
- The subject confirmed that he has not donated and will not donate semen or sperm while taking pomalidomide or during dose interruptions and that he will not donate semen or sperm for at least 28 days after the last dose of pomalidomide.
- The subject has not and will not donate blood while taking pomalidomide, during dose interruptions and for at least 28 days after the last dose of pomalidomide.
- The subject has not and will not break, chew, or open pomalidomide capsules at any point.
- The subject confirmed that he will return unused pomalidomide capsules to the study doctor.

2. I have provided the Pomalidomide Information Sheet to the subject.

Global PPP Pomalidomide Adult
Celgene Corporation

Protocol [#]
Version 4.0 – Approved: 30 October 2014
Effective Date: 19 December 2014

Do Not Dispense Pomalidomide if:

- The subject stated that he has or does not want to adhere to pregnancy precautions outlined within this PPP.

Counselor Name (Print): _____

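### The Appendix 15 counselling forms signed before each pomalidomide dispensing conflict with Appendix 4 on accepted contraceptive methods and on blood donation, and state only the pomalidomide part of the other restriction periods

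*Protocol*

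**What the plan says.** Two texts in the protocol govern pregnancy prevention, and both bind. Inclusion criterion I 07 (Section 5.1) and Appendix 4 (Section 10.4) set the trial's own contraception rules. Section 10.4.1 and footnote t of the Schedule of Activities also require compliance with the pomalidomide pregnancy prevention plan in Appendix 15, or with a country-specific plan where the sponsor does not supply the drug. Appendix 15, Section 1, has a trained counselor sign a sex-specific form before every dispensing.

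**Women, method.** The form (Appendix 15, Section 3.1) gives as highly effective "Hormonal (birth control pills, injections, implants, levonorgestrel-releasing intrauterine system [IUS], medroxyprogesterone acetate depot injections", with progesterone-only pills named separately in the same item, and lists a partner's vasectomy without qualification. In Section 10.4.2.2 the permitted combined hormonal routes do not include the oral one. Footnote c allows it only once pomalidomide has been stopped, because "combined oral contraceptive pills are not recommended because of the increased risk of venous thromboembolism in patients with multiple myeloma taking pomalidomide and dexamethasone". An azoospermic partner counts as highly effective only "provided that the partner is the sole sexual partner of the woman of childbearing potential and the absence of sperm has been confirmed".

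**Men, method.** Outside abstinence, the form (Appendix 15, Section 4) asks the man to confirm that he has "used a condom when engaging in sexual contact (including those who have had a vasectomy) with a pregnant female or FCBP". Section 10.4.2.3 asks for more: "Agree to use a male condom plus an additional contraceptive method with a failure rate of <1% per year".

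**Blood donation.** The female form reads "The subject has not and will not donate blood while taking pomalidomide, during dose interruptions and for at least 28 days" after the last pomalidomide dose, and the male form matches it. Section 10.4.4.3, headed as precautions related to pomalidomide, sets at least 3 months after study treatment.

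**Other periods.** The forms give at least 28 days after pomalidomide for contraception, breastfeeding and sperm donation. Appendix 4 gives 5 months after study treatment for female contraception. For male contraception, breastfeeding and sperm donation it pairs the 28-day or 4-week pomalidomide period with 5 months after isatuximab.

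**The concern.** The form is what the counselor works from when pomalidomide is released, and what the participant hears each cycle. Section 10.4.1 treats a teratogenic effect of the drug in humans as expected. If the form accepts a method that Appendix 4 does not, a correctly completed form does not show that the participant meets the protocol. If it states shorter or partial restriction periods, participants may act on those. What is at stake is the risk of fetal exposure and avoidable protocol deviations, not any estimate or test in the trial.

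**Working it through.** No formula or sample size is involved. The check sets the texts side by side.

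| Item | Appendix 15 form | Appendix 4 |
|---|---|---|
| Male method | Condom (or abstinence) | Condom plus a second method failing in <1% per year (or abstinence) |
| Female, pills | Birth control pills, unqualified | Combined oral pill not on the allowed list during pomalidomide; progestogen-only oral allowed |
| Female, partner vasectomy | Unqualified | Sole partner and confirmed absence of sperm |
| Blood donation | At least 28 days after pomalidomide | At least 3 months after study treatment |
| Female contraception, end | At least 28 days after pomalidomide | At least 5 months after study treatment |
| Male contraception, end | At least 28 days after pomalidomide | Later of 28 days after pomalidomide and 5 months after isatuximab |
| Breastfeeding | At least 28 days after pomalidomide | Later of 28 days after pomalidomide and 5 months after isatuximab |
| Sperm donation | At least 28 days after pomalidomide | 4 weeks after pomalidomide or 5 months after isatuximab |

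**Does the form catch a method that Appendix 4 does not accept?** Three cases.

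1. A man with a partner of childbearing potential uses a condom only. He meets the male form and fails Section 10.4.2.3. Appendix 15, Sections 2.3.2 and 2.5.2.2, repeat the condom-only rule, so the rest of the plan does not correct this.
2. A woman uses a combined oral pill and a condom. She has one method from each of the form's two lists and fails Section 10.4.2.2.
3. A woman relies on a partner's vasectomy, without confirmed absence of sperm, plus a condom. She meets the form; Section 10.4.2.2 would require an additional highly effective method.

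None of the three meets an explicit method-based refusal. The female refusal items cover pregnancy, missing tests, failure to use two methods before and during treatment, and unwillingness to follow the precautions in the plan. The male form has only the last. Both refer to the plan and neither refers to Appendix 4.

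**Blood donation.** Take 3 months as 91 days, an assumption (calendar months give 89 to 92 days). If pomalidomide is the last study drug, or all stop together: 91 − 28 = 63 days (range 89 − 28 = 61 to 92 − 28 = 64). Isatuximab does not explain the gap: Section 10.4.4.3 places the rule under pomalidomide precautions, and the Norwegian requirement (I 09 b and Section 10.8) counts the 3 months from pomalidomide itself.

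**Remaining periods.** The forms give a minimum for one drug and do not mention the others. Sections 6.5 and 7.1.1 allow isatuximab to continue after pomalidomide is stopped. The only period printed on the form can then run out while isatuximab is still being given.

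**The case against.** Several points on the other side are sound and limit the finding.

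- Appendix 15 is a single-drug plan and says at least 28 days. Appendix 4 keeps that floor and adds isatuximab, so observing the later date satisfies both texts. For contraception, breastfeeding and sperm donation the forms are incomplete rather than contradictory. Section 6.2.6 says the plan applies on top of the protocol, although only in its commercial-supply text and not on either form.
- A reader might infer that the shorter periods let a participant pass the dispensing check while in breach. They do not: at dispensing pomalidomide is still being given, and the female refusal item on methods covers the time before, during and between doses, not afterwards.
- A reader might also infer a one-versus-two-method conflict, because the visit check in Section 10.4.4.1 asks whether "she is continuing to use a highly effective form of contraception" while Appendix 15, Section 2.5.2.1, asks whether "she is continuing to use two reliable methods of birth control if not committing to complete abstinence". The documents do not support this. I 07 and Section 10.4.2.2 both require two methods, and the singular wording of a visit check is not a separate rule.
- Appendix 15, Section 2.3.1, tells combined-pill users to switch, and the form's list is headed as examples. This weakens the pill item but does not remove it, since the caveat is missing from the page that is signed.
- The form is not the only safeguard. I 07 applies at entry, the investigator confirms contraception with women of childbearing potential at each visit, and their pregnancy testing can run to 5 months after isatuximab. The visit check in Section 10.4.4 is written for women and does not cover the male method.
- The Pomalidomide Information Sheet and the consent form were not available to this review and may state the longer periods.
- Appendix 15 is not weaker throughout: its definition of childbearing potential does not exempt bilateral salpingectomy, while Section 10.4.2.1 does.

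**Conclusion.** The conflict is real and confined to sites that use the Appendix 15 forms.

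On method, a correctly completed form can coexist with a breach of Appendix 4. This is clearest for men using a condom alone, and narrower for women using a combined oral pill or relying on an unconfirmed partner vasectomy.

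On what participants are told, the blood-donation rule differs by about 63 days if pomalidomide is the last drug stopped or all stop together, and by more if isatuximab continues and the Section 10.4.4.3 wording is followed. The other periods are stated only in part, which matters most when isatuximab outlasts pomalidomide.

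The documents do not say how many participants are affected: the numbers of women of childbearing potential, of men with such partners, and of sites using a country-specific plan are not given. The trial's power, error rates and estimates are untouched. The passages should be reconciled; this review takes no view on which rule is right.

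**What to change.** Reconcile Appendix 15, Sections 2.3, 2.5, 3 and 4, with Sections 10.4.2.2, 10.4.2.3 and 10.4.4. Settle on one list of accepted methods, with any conditions, and one end point for each restriction, naming the drug from which it is counted. Print the agreed text on both counselling forms, for example as a trial-specific addendum, and have the refusal items refer to it. The sponsor's clinical and pregnancy-prevention teams decide which rule applies.

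The cost is amended wording and an addendum of about one page; no visits or procedures are added.
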